7.4.7 Follow-up

Subjects who complete 2 years of treatment or 32 cycles (whichever comes later) will move into the Follow-Up Phase and should be assessed every 12 weeks (± 30 days) by clinical standard of care MRI scans and clinical assessment to monitor disease status for up to 1 year or until they progress or death. After 1 year, the imaging and clinical assessment time point will occur every 6 months (± 30 days) until death. Follow-up may be done more frequently, at physician's discretion.

7.4.8 Survival Follow-up when off study

Once a subject is taken off study for any reason, the subject moves into the survival follow-up phase. Survival data will be collected from the medical record when available. When possible, the patient will be contacted by telephone approximately every 12 weeks to assess for survival status until death, withdrawal of consent, or the end of the study, whichever occurs first.

7.4.9 Second Course Phase (Retreatment Period)

Subjects who stop pembrolizumab with CR in the brain may be eligible for up to one year of additional pembrolizumab therapy if they progress systemically. This retreatment is termed the Second Course Phase of this study and is only available if the study remains open and the subject meets the following conditions:

Either

- Stopped initial treatment with pembrolizumab after attaining an investigator-determined confirmed CR, and
 - Was treated for at least 24 weeks with pembrolizumab before discontinuing therapy
 - Received at least two treatments with pembrolizumab beyond the date when the initial CR was declared

OR

- Had CR in the brain and stopped pembrolizumab treatment after 24 months of study therapy for reasons other than disease progression or intolerability

AND

- Experienced an investigator-determined confirmed radiographic disease progression after stopping their initial treatment with pembrolizumab
- Did not receive any anti-cancer treatment since the last dose of pembrolizumab
- Has a performance status of 0 or 1 on the ECOG Performance Scale
- Demonstrates adequate organ function as detailed in Section 5.2

Female subject of childbearing potential should have a negative serum or urine pregnancy test within 72 hours prior to receiving retreatment with study medication. If the urine test is positive, cannot be performed or cannot be confirmed as negative, a serum pregnancy test will be required.

- Female subject of childbearing potential should be willing to use 2 methods of birth control or be surgically sterile, or abstain from heterosexual activity for the course of the study through 120 days after the last dose of study medication. Subjects of child bearing potential are those who have not been surgically sterilized or have been free from menses for > 1 year.
- Male subject should agree to use an adequate method of contraception starting with the first dose of study therapy through 120 days after the last dose of study therapy.
- Does not have a history or current evidence of any condition, therapy, or laboratory abnormality that might interfere with the subject's participation for the full duration of the trial or is not in the best interest of the subject to participate, in the opinion of the treating investigator.

Subjects who restart treatment will be retreated at the same dose and dose interval as when they last received pembrolizumab. Treatment will be administered for up to one additional year.

Visit requirements are outlined in Section 6.0 – Schedule of Events.

7.5 Dose Modification

Adverse events (both non-serious and serious) associated with pembrolizumab exposure may represent an immunologic etiology. These adverse events may occur shortly after the first dose or several months after the last dose of treatment. Pembrolizumab must be withheld for drug-related toxicities and severe or life-threatening AEs as per Table 6 below.

Table 6 Dose Modification and Toxicity Management Guidelines for Immune-related AEs Associated with Pembrolizumab

General instructions:

Corticosteroid taper should be initiated upon AE improving to Grade 1 or less and continue to taper over at least 4 weeks. For situations where pembrolizumab has been withheld, pembrolizumab can be resumed after AE has been reduced to Grade 1 or 0 and corticosteroid has been tapered. Pembrolizumab should be permanently discontinued if AE does not resolve within 12 weeks of last dose or corticosteroids cannot be reduced to ≤ 10 mg prednisone or equivalent per day within 12 weeks. For severe and life-threatening irAEs, IV corticosteroid should be initiated first followed by oral steroid. Other immunosuppressive treatment should be initiated if irAEs cannot be controlled by corticosteroids.

Immune-related AEs	Toxicity grade or conditions (CTCAEv4.0)	Action taken to pembrolizumab	irAE management with corticosteroid and/or other therapies	Monitor and follow-up
Pneumonitis	Grade 2	Withhold	
 Administer corticosteroids (initial dose of 1-2 mg/kg prednisone or equivalent) followed by taper 	
 Monitor participants for signs and symptoms of pneumonitis Evaluate participants with suspected pneumonitis with radiographic imaging and initiate corticosteroid treatment Add prophylactic antibiotics for opportunistic infections
	Grade 3 or 4, or recurrent Grade 2	Permanently discontinue		
Diarrhea / Colitis	Grade 2 or 3	Withhold	
 Administer corticosteroids (initial dose of 1-2 mg/kg prednisone or equivalent) followed by taper 	
 Monitor participants for signs and symptoms of enterocolitis (ie, diarrhea, abdominal pain, blood or mucus in stool with or without fever) and of bowel perforation (ie, peritoneal signs and ileus). Participants with \geq Grade 2 diarrhea suspecting colitis should consider GI consultation and performing endoscopy to rule out colitis. Participants with diarrhea/colitis should be advised to drink liberal quantities of clear fluids. If sufficient oral fluid intake is not feasible, fluid and electrolytes should be substituted via IV infusion.
	Grade 4	Permanently discontinue		
AST/ALT elevation or Increased bilirubin	Grade 2	Withhold	
 Administer corticosteroids (initial dose of 0.5- 1 mg/kg prednisone or equivalent) followed by taper 	
 Monitor with liver function tests (consider weekly or more frequently until liver enzyme value returned to baseline or is stable)
	Grade 3 or 4	Permanently discontinue	
 Administer corticosteroids (initial dose of 1-2 mg/kg prednisone or equivalent) followed by taper 	

Type 1 diabetes mellitus (T1DM) or Hyperglycemia	Newly onset T1DM or Grade 3 or 4 hyperglycemia associated with evidence of β -cell failure	Withhold	
 Initiate insulin replacement therapy for participants with T1DM Administer anti-hyperglycemic in participants with hyperglycemia 	
 Monitor participants for hyperglycemia or other signs and symptoms of diabetes.
Hypophysitis	Grade 2	Withhold	
 Administer corticosteroids and initiate hormonal replacements as clinically indicated. 	
 Monitor for signs and symptoms of hypophysitis (including hypopituitarism and adrenal insufficiency)
	Grade 3 or 4	Withhold or permanently discontinue ¹		
Hyperthyroidism	Grade 2	Continue	
 Treat with non-selective beta-blockers (eg, propranolol) or thionamides as appropriate 	
 Monitor for signs and symptoms of thyroid disorders.
	Grade 3 or 4	Withhold or permanently discontinue ¹		
Hypothyroidism	Grade 2-4	Continue	
 Initiate thyroid replacement hormones (eg, levothyroxine or liothyronine) per standard of care 	
 Monitor for signs and symptoms of thyroid disorders.
Nephritis and Renal dysfunction	Grade 2	Withhold	
 Administer corticosteroids (prednisone 1-2 mg/kg or equivalent) followed by taper. 	
 Monitor changes of renal function
	Grade 3 or 4	Permanently discontinue		
Myocarditis	Grade 1 or 2	Withhold	
 Based on severity of AE administer corticosteroids 	
 Ensure adequate evaluation to confirm etiology and/or exclude other causes
	Grade 3 or 4	Permanently discontinue		
All other immune-related AEs	Intolerable/persistent Grade 2	Withhold	
 Based on type and severity of AE administer corticosteroids 	
 Ensure adequate evaluation to confirm etiology and/or exclude other causes
	Grade 3	Withhold or discontinue based on the type of event. Events that require discontinuation include and not limited to: Guillain-Barre Syndrome, encephalitis		
	Grade 4 or recurrent Grade 3	Permanently discontinue		

1. Withhold or permanently discontinue pembrolizumab is at the discretion of the investigator or treating physician.

NOTE:

For participants with Grade 3 or 4 immune-related endocrinopathy where withhold of pembrolizumab is required, pembrolizumab may be resumed when AE resolves to \leq Grade 2 and is controlled with hormonal replacement therapy or achieved metabolic control (in case of T1DM).

Dosing interruptions are permitted in the case of medical/surgical events or logistical reasons not related to study therapy (e.g., elective surgery, unrelated medical events, subject vacation,

and/or holidays), not to exceed two cycles. Subjects should be placed back on study therapy within 3 weeks of the scheduled interruption in all cases other than when pembrolizumab is stopped for craniotomy to confirm progression or unless otherwise discussed with the Sponsor. The reason for interruption should be documented in the subject's study record.

There is limited data regarding optimal therapy for refractory and/or persistent side effects from pembrolizumab (after discontinuation of pembrolizumab and initiation of steroids). These subjects will be managed according to best available practice and guidelines/treatment algorithms provided by the drug manufacturer Merck & Co. This may include but not limited to the use of drugs such as [infliximab](#) (5 mg/kg). If symptoms persist after the first infliximab dose, a second dose of infliximab (5 mg/kg) may be repeated two weeks after the initial dose.

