5.3 Subject Withdrawal/Discontinuation Criteria

Subjects may withdraw consent at any time for any reason or be dropped from the trial at the discretion of the investigator should any untoward effect occur. In addition, a subject may be withdrawn by the investigator or the Sponsor if enrollment into the trial is inappropriate, the trial plan is violated, or for administrative and/or other safety reasons.

A subject must be discontinued from the trial for any of the following reasons:

- The subject or legal representative (such as a parent or legal guardian) withdraws consent.
- Persistent radiographic progression confirmed by tissue biopsy.
- Persistent radiographic progression if subject is not a candidate for repeat surgery or subject refuses a repeat biopsy to pathological confirmed of disease progression

Note: A subject may be granted an exception to continue on treatment with confirmed radiographic progression if clinically stable or clinically improved, at the discretion of the treating physician. Please see Section 7.4.9

- Unacceptable adverse experiences as described in Section 9.0
- Miss two consecutive treatments for any reason other than surgery
- Intercurrent illness that prevents further administration of treatment
- Investigator's decision to withdraw the subject
- The subject has a confirmed positive serum or urine pregnancy test. If the urine test is positive, cannot be performed or cannot be confirmed as negative, a serum pregnancy test will be required. Noncompliance with trial treatment or procedure requirements
- The subject is lost to follow-up
- Completed 24 months of uninterrupted treatment with pembrolizumab or 35 administrations of study medication, whichever is later.

Note: 24 months of study medication is calculated from the date of first dose. Subjects who stop pembrolizumab after 24 months may be eligible for up to one year of additional study treatment if they progress after stopping study treatment provided they meet the requirements detailed in Section 5.4.1

- Administrative reasons

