7.1 Trial Treatments

The treatment to be used in this trial is outlined below in Table 4

Table 4 Trial Treatment

Drug	Dose/Potency	Dose Frequency	Route of Administration	Regimen/Treatment Period	Use
Therapeutic Agent					
Pembrolizumab	200 mg	Every 3 weeks (+15 days)	IV infusion	Day 1 of each 3 week cycle	Experimental
Imaging Agent					
Ferumoxylol		Baseline, 12 weeks post radiation, anytime there is suspected radiographic progression and 6 weeks after suspected radiographic progression (± 15 days).	IV infusion	Baseline, 12 weeks post radiation, anytime there is suspected radiographic progression and 6 weeks after suspected radiographic progression (± 15 days).	

Trial treatment should begin on the day of randomization or as close as possible to the date on which treatment is allocated/assigned.

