- Independent risk factors include certain medications such as anticonvulsants, sulfonamides, aminopenicillins, allopurinol, and NSAIDs. Non-medication triggers include infection, contrast media, and vaccinations.
- Maligancy is associated with an increased mortality rate in patients with SJS and TEN.

For signs or symptoms of SJS or TEN, withhold Pembrolizumab and refer the patient for specialized care for assessment and treatment. If SJS or TEN is confirmed, permanently discontinue Pembrolizumab.

- **Immune-mediated myocarditis**

A total of 6 cases of myocarditis have been reported in patients treated with pembrolizumab in clinical trials or in an expanded access program. There were 1 fatal case reported in a clinical trial.

A search of the literature identified neither background incidence rates nor prevalence of myocarditis specifically among cancer patients. Immune-mediated myocarditis should be suspected if other causes of myocarditis, such as infection or prior radiation therapy, have been excluded. Risk factors include certain medications and treatment modalities such as radiation, anthracycline, alkylating agents and most recently checkpoint inhibitors. For suspected immune-mediated myocarditis, ensure adequate evaluation to exclude other etiologies, and administer corticosteroids.

- **Management of Infusion Reactions:** Signs and symptoms usually develop during or shortly after drug infusion and generally resolve completely within 24 hours of completion of infusion.

Table 8 below shows treatment guidelines for subjects who experience an infusion reaction associated with administration of pembrolizumab (MK-3475).

Table 8 Infusion Reaction Treatment Guidelines

NCI CTCAE Grade	Treatment	Premedication at subsequent dosing
Grade 1 Mild reaction; infusion interruption not indicated; intervention not indicated	Increase monitoring of vital signs as medically indicated until the subject is deemed medically stable in the opinion of the investigator.	None
Grade 2 Requires infusion interruption but responds promptly to symptomatic treatment (e.g., antihistamines, NSAIDs, narcotics, IV fluids);	Stop Infusion and monitor symptoms. Additional appropriate medical therapy may include but is not limited to: IV fluids Antihistamines NSAIDS	Subject may be premedicated 1.5h (± 30 minutes) prior to infusion of Pembrolizumab (MK-3475) with: Diphenhydramine 50 mg po (or equivalent dose of antihistamine).

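### Section 7.5 permits pembrolizumab to restart at Grade 1 myocarditis, a grade at which the myocarditis row of Table 6 requires withholding (minor safety inconsistency)

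*Combined protocol and SAP*

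**What the plan says.** Section 7.5 makes Table 6 binding: "Pembrolizumab must be withheld for drug-related toxicities and severe or life-threatening AEs as per Table 6 below". The myocarditis row withholds at Grade 1 or 2 and discontinues permanently at Grade 3 or 4. It ties corticosteroid use to the severity of the event, so steroids are not automatic.

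The general instructions at the head of the table apply to all withheld events:

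- Taper: "Corticosteroid taper should be initiated upon AE improving to Grade 1 or less and continue to taper over at least 4 weeks".
- Restart: "pembrolizumab can be resumed after AE has been reduced to Grade 1 or 0 and corticosteroid has been tapered".
- Time limit: "Pembrolizumab should be permanently discontinued if AE does not resolve within 12 weeks of last dose".

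One departure from the restart rule is written out, in the NOTE under the table: "For participants with Grade 3 or 4 immune-related endocrinopathy where withhold of pembrolizumab is required, pembrolizumab may be resumed when AE resolves to" Grade 2 or lower, provided the event is controlled by hormone replacement or, for type 1 diabetes, metabolically. There is no such note for myocarditis.

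Section 9.5.2 covers work-up and treatment only: "For suspected immune-mediated myocarditis, ensure adequate evaluation to exclude other etiologies, and administer corticosteroids". It gives no restart grade. Section 5.3 lists among the reasons for mandatory discontinuation: "Miss two consecutive treatments for any reason other than surgery". The rechallenge item in Table 9 (section 9.6) requires advance approval where the event was serious and possibly drug-caused, or where re-exposure carries additional potential significant risk.

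**The concern.** Take a subject whose myocarditis was Grade 2, is now Grade 1, and whose steroid taper is finished. The row says withhold at this grade; the general instruction says dosing may resume. The protocol does not say which prevails, so two investigators could act differently on the same patient and both cite section 7.5.

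What is at stake is subject safety, not inference. Section 9.5.2 reports 6 myocarditis cases with pembrolizumab, one of them fatal in a clinical trial. Myocarditis is also the only event in Table 6 for which Grade 1 is named as a withhold grade. A restart rule that can undo that extra caution should not be left to interpretation.

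**Working it through.** There is no planned figure to reproduce. The check compares the withhold grades in each row of Table 6 with the general restart set, {0, 1}.

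| Table 6 row | Withhold grades | Overlap with {0, 1} |
|---|---|---|
| Pneumonitis | 2 | none |
| Diarrhea/colitis | 2, 3 | none |
| AST/ALT or bilirubin | 2 | none |
| Type 1 diabetes/hyperglycemia | new onset (ungraded); 3, 4 | none by grade |
| Hypophysitis | 2, 3, 4 | none |
| Hyperthyroidism | 3, 4 | none |
| Hypothyroidism | never withheld | not applicable |
| Nephritis | 2 | none |
| Myocarditis | 1, 2 | **1** |
| All other | 2, 3 | none |

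(Grades where the row offers a choice of withholding or discontinuing are counted as withhold grades.)

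**Count.** There are 10 rows, and 9 withhold at some point. One of those 9 overlaps the general restart rule: {1, 2} ∩ {0, 1} = {1}, myocarditis. Under the endocrinopathy NOTE the restart set is {0, 1, 2}, and hypophysitis overlaps it at Grade 2. That overlap is evidently deliberate, because the NOTE sets its own threshold and adds a control condition.

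**Grades left for dosing.** For myocarditis, Grades 1 and 2 are withheld and Grades 3 and 4 are discontinued. Grade 0 is the only grade in Table 6 with no withhold or discontinue action.

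**Does Table 9 close the gap?** In part. It covers the two situations described above. What remains is a non-serious event where re-exposure is not judged to carry additional significant risk. Such an event is governed by section 7.5 alone.

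**Does section 5.3 close the gap?** Not always. Put the last dose at day 0, so that the next doses fall due on days 21 and 42. Suppose the day-21 dose is missed.

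- With the 7-day delay allowed in section 7.2, the second dose can be given up to 42 + 7 = day 49.
- With the +15-day window in Table 4, it can be given up to 42 + 15 = day 57.
- For a subject given steroids, allow the minimum 4-week (28-day) taper: 49 − 28 = day 21, and 57 − 28 = day 29.

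So a steroid-treated event that falls to Grade 1 by day 21 (or day 29, with the wider window) could be re-dosed at Grade 1 after one missed treatment. This timing applies only to subjects given steroids. Without steroids there is no taper to wait for.

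**Does the 12-week limit close the gap?** No. It says when to stop permanently, not when restart is allowed, and it does not define resolution as Grade 0. Twelve weeks is day 84, later than day 57, so the two-missed-treatments rule would normally act first.

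**The case against.** The strongest reply is that the two rules address different moments: the row is a trigger at onset, and the general instruction is a release afterwards. A stricter trigger with a looser release is not in itself a contradiction, and the endocrinopathy NOTE shows that Table 6 can allow restart at a withhold grade.

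This reading is possible but does not settle the matter. If an event already at Grade 1 satisfies the restart wording, a Grade 1 myocarditis given no steroids could be released almost as soon as it is withheld, leaving the Grade 1 trigger with little effect. If an actual reduction is needed, a Grade 1 event must wait for Grade 0 while a Grade 2 event may be re-dosed at Grade 1, so the milder event faces the stricter rule. Where the authors wanted a special restart threshold, they wrote one; for myocarditis they did not.

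Other parts of the reply stand. Restart is permissive, the row requires the cause to be evaluated, and the investigator may withdraw a subject. No passage sets Grade 0 as the restart grade. Section 7.2 defers dose discontinuations to manufacturer guidelines that are not reproduced, so the intended threshold cannot be established from the documents. Section 9.5.2 gives 6 cases without a denominator, so no expected number among 20 subjects can be computed.

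A reader might infer that the protocol directs re-dosing during active myocarditis, or that nothing controls rechallenge. Neither is supported: section 7.5 allows restart without requiring it and makes it conditional on the taper, and Table 9's approval requirement still applies.

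**Conclusion.** The inconsistency is real and minor. Grade 1 myocarditis falls under both a mandatory withhold and a permitted restart, and no other row has this overlap with the general rule. The clear case is improvement from Grade 2 to Grade 1 with the taper complete. The case of a Grade 1 event without steroids is arguable, because it turns on how the restart wording is read. The exposure is limited to non-serious events not judged to carry additional significant risk.

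The conclusion assumes that the protocol text is the operative instruction and that the row does not silently override the general rule; the protocol states no order of precedence. With few cases expected in 20 subjects, and the primary sensitivity and specificity analysis untouched, the documents do not support treating this as a major safety defect or as a threat to the trial's results.

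**What to change.** Add one sentence to the myocarditis row of Table 6: *Resume only after resolution to Grade 0 and completion of any corticosteroid taper.* Grade 0 is a clinical choice, supported by its being the only grade the row leaves free of a withhold or discontinue action. If the sponsor intends restart at Grade 1, the row should say so and give the conditions.

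Nothing else needs to change. The 12-week limit, the two-missed-treatments rule in section 5.3 and the approval triggers in Table 9 already apply and need no restatement.

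The cost is one sentence. The downside falls on a subject with persistent Grade 1 myocarditis, who would stay off pembrolizumab and might have to leave the trial under section 5.3.

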7.6 Trial Blinding/Masking

This is an open-label pilot trial; therefore, the Sponsor, investigator and subject will know the treatment administered.

7.7 Randomization or Treatment Allocation

N/A

7.8 Stratification

N/A

7.9 Concomitant Medications/Vaccinations (allowed & prohibited)

Medications or vaccinations specifically prohibited in the exclusion criteria are not allowed during the ongoing trial. If there is a clinical indication for one of these or other medications or vaccinations specifically prohibited during the trial, discontinuation from trial therapy or vaccination may be required. The investigator should discuss any questions regarding this with the Merck Clinical team. The final decision on any supportive therapy or vaccination rests with the investigator and/or the subject's primary physician.

